7.2 Secondary Efficacy Analyses

7.2.1 *Difference between Period 2 and Period 1 Change from Baseline in VO₂MAX*

The first secondary efficacy endpoint is the change from Baseline of VO₂MAX at the end of Period 1 compared to the change from Baseline at the end of Period 2. This will be analyzed using an ANCOVA with covariates of baseline VO₂MAX and the Period-mean plasma PEX level for the Completer Population. The estimated mean change in VO₂MAX from Baseline to Period 1 and to Period 2 and the difference between Period 1 and Period 2 will be presented along with a 95% confidence interval and the p-value. This analysis will be repeated for the MITT, and will include any imputed change in VO₂MAX as in the primary analysis.

Example SAS code is shown below:

```
proc mixed data=dataP1P2;  
  class Period;  
  model CHG=BASE PEXP1P2 Period/ solution cl;  
  lsmeans Period/ cl diffs;  
  estimate "Period 2 vs. Period 1" Period -1 1/ cl;  
run;
```

7.2.2 *Change from Baseline in VO₂MAX at the end of Period 1*

The second secondary efficacy endpoint is the change from Baseline of VO₂MAX at the end of Period 1. Similar to the primary efficacy endpoint, this will be analyzed using an ANCOVA with covariates of baseline VO₂MAX and the Period 1 mean plasma PEX level for the Completer Population. This will be repeated for the MITT, including any imputed change in VO₂MAX values for patients who did not complete the study to the end of Period 1. Descriptive statistics of the Baseline value, VO₂MAX at the end of Period 1 and the change from Baseline to end of Period 1 will be presented for the Completer Population and the MITT Population.

7.2.3 *Change from Baseline in 6MWT at the end of Period 2*

The change from Baseline in the 6MWT at the end of Period 2 will be analyzed using an ANCOVA with covariates of baseline VO₂MAX and the Period 2 mean plasma PEX level. This will be presented for the Completer Population and repeated for the MITT including any imputed change from Baseline values for patients who did not complete the study to the end of Period 2.

7.2.4 *Difference between Period 2 and Period 1 Change from Baseline in 6MWT*

The change from Baseline in the 6MWT at the end of Period 1 compared to the change from Baseline at the end of Period 2 will be analyzed using an ANCOVA with covariates of baseline VO₂MAX and the Period-mean plasma PEX level Completer Population and repeated for the MITT.

7.2.5 *Change from Baseline in 6MWT at the end of Period 1*

The change from Baseline in the 6MWT at the end of Period 1 will be analyzed using an ANCOVA with covariates of baseline VO_{2MAX} and the Period 1 mean plasma PEX level. This will be presented for the Completer Population and repeated for the MITT including any imputed change from Baseline values for patients who did not complete the study to the end of Period 1.

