2.8 STUDY RATIONALE

This is an open-label, phase II study to confirm the optimal dosing regimen of PEX for use in a future phase III study in patients with HCM. The previous study [Abozguia, 2010] in HCM patients demonstrated that a safe and effective plasma concentration for PEX was 150-600 ng/mL. However, a more refined dosing study to evaluate safety and efficacy at low (100-300 ng/mL) and high (300-500 ng/mL) plasma PEX levels has not yet been performed. Potentially, equal efficacy with improved safety could be achieved at lower concentrations of PEX.

A population pharmacokinetic (PK) evaluation of the PK data from the PEX-TQT study was done to identify and characterize patient factors influencing PEX PK and the magnitude of unexplained PK variability [Mould, 2016]. Application of this newly developed model compared to a previously published model [Hussein *et al.*, 2001] showed the new model better describes PEX PK, particularly in extensive metabolizer (EM) and intermediate metabolizer (IM) groups.

The 2-compartment PK model developed from this exercise was used to predict drug exposures after single and multiple doses of PEX 70, 140, and 280 mg in all CYP2D6 genotypes [Mould, 2016]. Simulations of multiple dose administrations demonstrated that therapeutic levels of PEX in the range of 150-600 ng/mL for all the CYP2D6 genotypes eligible could be achieved in this study with doses of 70 to 280 mg daily. Figure 2.1 shows the initial response to 70 mg daily in IM, EM, and PM subjects, and clearly shows that all subjects, including phenotypic PM subjects can be safely dosed through two weeks without reaching

excessive PEX levels. However, conservatively, a blood sample to measure PEX and CIS levels will be obtained at day 8 to withdraw phenotypic PMs from the study. Then starting on day 15, PEX levels will continue to be measured every other week (Weeks 2, 4, 6, 8, 10, 12 and 14) in order to guide dose adjustment and to achieve the desired plasma concentrations. The following doses are expected to produce therapeutic concentrations in the majority of patients (PMs are being excluded from the study):

- Intermediate Metabolizers (IM): 70 to 140 mg daily
- Extensive Metabolizers (EM): 140 to 210 mg daily
- Ultra-rapid Metabolizers (UM): May require maximum doses of 210 (Period 1) or 280 (Period 2) mg daily. These subjects may not reach the target therapeutic level.

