2.8.4 Monitoring of Systemic Levels and Dose Adjustment of Perhexiline

Because of the potential safety risk from study-drug accumulation, a dose-adjustment algorithm will be used (see section 4.4.3) based on the systemic plasma levels of PEX determined from regular blood sampling throughout the dosing regimens in Periods 1 and 2. The objective of the dose adjustment decisions will be to achieve steady-state systemic plasma levels of PEX within the recommended target therapeutic range of either 100-300 ng/mL in Period 1 or 300-500 ng/mL in Period 2.

Considering the intra-day C_{min}-C_{max} range of plasma concentrations projected by PK simulations (section 2.8) it is proposed that the blood sampling timepoints will be scheduled approximately 12h following study drug dosing on the previous day in order to coincide with the approximate intra-day mean systemic plasma level of PEX.

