2.1.2 Secondary Objectives

The secondary objectives of the study are to evaluate:

- The ascending dose-response effect on the change from Baseline of VO_{2MAX} in patients with HCM and moderate-to-severe heart failure with preserved LV function following repeat dosing with PEX for 112 days.
- The electrocardiographic (ECG) response, tolerability and safety of orally administered PEX in patients with HCM and moderate-to-severe heart failure with preserved LV function following repeat dosing with PEX for 112 days.

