12 CHANGES FROM PROTOCOL-SPECIFIED STATISTICAL ANALYSES

1. Added Modified Intention to Treat Population as a sensitivity analysis population for efficacy analyses.
2. Added inclusion of early withdrawal efficacy assessments in efficacy analyses that use the MITT Population.
3. The protocol specified that each analysis would be performed using a t-test. During preparation of the statistical analysis plan, it was decided to change this to analysis of covariance (ANCOVA). The intention was to allow covariate adjustment for a Baseline value, to adjust for baseline severity, and in some analyses the plasma PEX level, to adjust for some measure of study medication intake level.

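### The Period 2 versus Period 1 comparison adjusts for the plasma perhexiline level that separates the periods, and its example code ignores that each patient contributes two records

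*SAP*

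**What the plan says.** Protocol 2.8.4 sets a "target therapeutic range of either 100-300 ng/mL in Period 1 or 300-500 ng/mL in Period 2". Protocol 2.8 explains that no study has yet been done to "evaluate safety and efficacy at low (100-300 ng/mL) and high (300-500 ng/mL) plasma PEX levels", and SAP 2.1.2 lists as a secondary objective "The ascending dose-response effect on the change from Baseline of" VO2MAX.

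SAP 7.2.1 is the analysis that serves this objective. It is an ANCOVA of change in VO2MAX using both periods, with baseline VO2MAX and "the Period-mean plasma PEX level for the Completer Population" as covariates. The example PROC MIXED step has Period as its only class variable, the statement "model CHG=BASE PEXP1P2 Period/ solution cl", and an estimate of Period 2 minus Period 1. It contains no patient identifier and no REPEATED or RANDOM statement.

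SAP 7.2.4 gives the 6MWT comparison the same covariates ("the Period-mean plasma PEX level Completer Population and repeated for the MITT") and shows no code. SAP 12 says the t-tests were replaced by ANCOVA to adjust for baseline and, "in some analyses the plasma PEX level, to adjust for some measure of study medication intake level". Neither document plans an unadjusted or paired test of Period 2 against Period 1.

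**The concern.** There are two separate faults.

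1. **The covariate is the exposure under study.** Drug intake is not a nuisance variable in this comparison; it is what distinguishes the periods. With Period and period-mean PEX in one model, the Period coefficient answers whether the periods differ when plasma levels are the same. The objective asks whether the higher range does better than the lower one. If the drug acts through its concentration, 7.2.1 would tend to report no difference between periods. Protocol 2.8 raises the possibility that lower levels are equally effective, so such a null could be misread as support for it when the Phase 3 regimen is chosen.

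2. **The two records of a patient are treated as independent.** Each completer supplies a Period 1 and a Period 2 change measured against the same baseline. Ignoring the pairing gives up the main efficiency of a within-patient design.

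SAP 7.1 and 7.2.2 do not share the first fault. Each covers a single period, so centring on that period's PEX leaves the mean change where it was.

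**Working it through.** **Inputs from the documents** (Protocol 8.2, SAP 11): mean changes 1.2 (Period 1) and 2.0 (Period 2) mL O2/kg/min, so a difference of 0.8; SD 2.5 in each period; n = 30; two-sided alpha 0.05.

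**Assumptions, because the documents give no values:** mean PEX 200 and 400 ng/mL (the target midpoints); PEX SD 50/60 or 80/100 in Periods 1/2; PEX correlation between periods 0, 0.5 or 0.8; within-patient correlation of the two changes rho = 0.5, varied from 0.3 to 0.7.

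**Step 1: the plan's own figures.** A one-sample t-test (noncentral t) gives 98.8% power for a mean of 2.0 and 71.9% for a mean of 1.2. These match the stated >95% and 72%. The 72% is thus the power for Period 1 change against zero, which is the analysis in 7.2.2. No power is stated for the Period contrast in 7.2.1.

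**Step 2: what the adjusted contrast estimates.** In an ANCOVA of this form,

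adjusted difference = (difference in mean change) − b × (difference in mean PEX),

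where b is the pooled within-period slope of change on PEX.

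- Gain linear in PEX: b = 0.8/200 = 0.004 per ng/mL, so the contrast is 0.8 − 0.004 × 200 = 0. The line is 0.4 + 0.004 × PEX. At the pooled mean of 300 ng/mL both LS means are 0.4 + 1.2 = 1.6, whereas 7.2.2 and 7.1 would report about 1.2 and 2.0.
- Gain unrelated to PEX: b = 0, so the contrast is 0.8 and unbiased, but Period and PEX are strongly collinear. With a common PEX SD of s, variance inflation is 1 + 100²/s², which is 5.0, 2.6 and 2.0 for s = 50, 80 and 100.

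**Step 3: the cost of ignoring pairing, with PEX left out.**

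- Independent records: SE = 2.5 × √(2/30) = 0.645 at any rho.
- Paired: SE = 2.5 × √(2(1 − rho)) / √30, which is 0.540, 0.456 and 0.354 at rho 0.3, 0.5 and 0.7. Power for 0.8 is 30%, 40% and 59%.
- At rho 0.5 the unpaired SE is 0.645/0.456 = 1.41 times too large. Simulated type I error of the unpaired model is 2.1%, 0.7% and 0.1% at rho 0.3, 0.5 and 0.7.

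**Step 4: simulation at rho 0.5** (3,000 trials per setting; least squares on 60 records, equivalent to the SAP step).

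| Analysis | Gain linear in PEX | Gain unrelated to PEX |
|---|---|---|
| SAP 7.2.1 model | estimate about 0.0, SE 0.97-1.38, significant in 3-8% | estimate 0.77-0.81, power 8-12% |
| PEX dropped, records unpaired | SE 0.64, power 14-17% | SE 0.64, power 14-17% |
| Paired | estimate 0.80, SE 0.45, power about 40% | power about 40% |

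Over rho 0.3 to 0.7, the SAP contrast under a linear gain is significant in 1.9-9.3% of trials.

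**Step 5: less separation.** Protocol 2.8 says of ultra-rapid metabolizers, "These subjects may not reach the target therapeutic level". With mean PEX 200 and 330 ng/mL the contrast under a linear gain is still about 0 and is significant in 2-6% of trials.

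**Step 6: does the PEX slope rescue the analysis?** The `solution cl` options would print it. It is unbiased (0.39-0.41 per 100 ng/mL against a true 0.40) but significant in only 11-24% of trials, and the SAP text gives it no role.

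**The case against.** - **The unadjusted means will be visible.** SAP 7.1 and 7.2.2 plan descriptive statistics of change in each period, for completers and for the MITT, so a reader would see about 1.2 and 2.0. This is correct. What is lost is a valid interval and p-value for the difference, and the formal output would contradict the descriptive tables.
- **An expectation of zero is a limiting case.** It needs a linear effect and a period-mean PEX that measures effective exposure without error. The covariate averages a few samples, and the Period 1 samples include the fixed starting dose. With reliability λ the formula in step 2 becomes 0.8(1 − λ): 0.16, 0.32 and 0.48 at λ = 0.8, 0.6 and 0.4. Simulation gave 0.17, 0.31-0.34 and 0.49-0.50. A response step at 300 ng/mL gave 0.55 or 0.19, depending on PEX spread. This stands: the bias may be partial. Rejection stayed at about 4-7% throughout, so the loss of power does not depend on the limiting case.
- **The code is only an example, and ignoring pairing is conservative.** Both are true. With positive correlation the second fault cannot create a false difference, and alone it would be a specification gap. The first fault rests on the SAP text, not the code. That text also rules out reading the undefined variable PEXP1P2 as one mean over both periods.
- **It is a secondary endpoint in a single-arm Phase 2 study, and the repaired test has only modest power.** Also true. But 7.2.1 calls it the first secondary endpoint, and it is the only formal VO2MAX comparison of the two exposure ranges.

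**Conclusion.** The concern holds. As written, 7.2.1 estimates the Period difference at equal plasma PEX, which is not the low-versus-high comparison the objective calls for. At the plan's own effect sizes it would detect that difference in roughly 3-12% of trials, against about 40% for a paired analysis (30-59% over rho 0.3 to 0.7). Under a linear, well-measured exposure effect the contrast centres on zero at any sample size; with noisy exposure or a step response the bias is partial and the power remains very low. The numerical sizes depend on the assumed PEX means, PEX spread and correlations. The direction follows from the model.

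The covariate fault applies equally to 7.2.4. The missing patient term is shown in the 7.2.1 code; in 7.2.4 the text simply does not provide one. The primary endpoint is unaffected. This should be corrected before database lock, up to which SAP 1 permits revision.

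**What to change.** In 7.2.1 and 7.2.4:

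1. Remove the PEX covariate from the Period comparison. Fit Period and baseline with `class Period patient; repeated Period / subject=patient type=un;`. For completers this is essentially a paired t-test. In the MITT repeat it keeps patients with only one period, whom a paired t-test would drop. State the denominator degrees-of-freedom method, and name the baseline variable explicitly in 7.2.4, where the SAP currently gives baseline VO2MAX for a 6MWT outcome.
2. Put exposure-response in a separate model with PEX level and a patient effect, labelled exploratory.
3. State that both analyses mix exposure with time and order, because the periods run in a fixed sequence without a control arm. SAP 8.2 gives such a caveat for adverse events; 7.2.1 and 7.2.4 give none.
4. State that a non-significant Period difference is not evidence of equal efficacy, given power of about 40% at a within-patient correlation of 0.5.

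For consistency, name the same patient term where HbA1c (8.4) and QTcF (8.6) are compared between periods. Those sections show no code and no PEX covariate, so that is a matter of specification only.

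The cost is SAP wording and a few lines of code, with no new data. The one loss is that the PEX slope moves to an exploratory table.

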3.1.2 Secondary efficacy variables

Change from Baseline in VO₂MAX to end of Period 1 compared to Period 2 and Change from Baseline in VO₂MAX to end of Period 1

The change and percent change from Baseline in VO₂MAX to the end of study-drug dosing Period 1 and Period 2 will be derived:

Change at Period 1 = Period 1 VO₂MAX – Baseline VO₂MAX

Percent Change at Period 1 = (Period 1 VO₂MAX – Baseline VO₂MAX)/Baseline VO₂MAX

Change at Period 2 = Period 2 VO₂MAX – Baseline VO₂MAX

Percent Change at Period 2 = (Period 2 VO₂MAX – Baseline VO₂MAX)/Baseline VO₂MAX

As in the primary endpoint, the VO₂MAX at the Day 1 assessment will be regarded as Baseline.

In the same way as for the primary endpoint, if the patient withdraws from the study early, but provides an unscheduled or early end-of-Period 1 or end-of-Period 2 VO₂MAX assessment then this VO₂MAX assessment will be used in the derivation of efficacy endpoints. Only if the unscheduled or early end-of-Period 1 or end-of-Period 2 VO₂MAX assessment is within ±7 days of the intended target assessment (Period 1 target = Day 57; Period 2 target = Day 113), relative to Day 1, will the derived change in VO₂MAX values be used in the principal analysis of this endpoint using the Completer Population (see sections 7.2.1 and 7.2.2).

6 Minute Walk Test

A 6-minute walk test (6MWT) was to be performed at the Baseline (Day 1) assessment and repeated at the end of Period 1 (Week 8) and the end of Period 2 (Week 16).

The change and percent change from Baseline at the end of study-drug dosing Period 2 and the change and percent change from Baseline at the end of study-drug dosing Period 1 will be derived, taking the Day 1 assessment as Baseline.

If a patient withdraws from the study early, but provides an end-of-Period 1 or end-of-Period 2 assessment then this assessment will be used in the derivation of the efficacy endpoints. As in the analysis of the primary endpoint, only if the unscheduled or early end-of-Period 1 or end-of-Period 2 6MWT assessment is within ±7 days of the intended target assessment (Period 1 target = Day 57; Period 2 target = Day 113), relative to Day 1, will the derived change in 6MWT values be used in the principal analysis of this endpoint using the Completer Population (see section 7.2.3 and 7.2.4).

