7 ANALYSIS OF EFFICACY

7.1 Primary Efficacy Analysis

The primary endpoint is the change from Baseline of VO_{2MAX} at the end of Period 2. This will be analyzed using an Analysis of Covariance (ANCOVA) with covariates of baseline VO_{2MAX} and the mean plasma PEX level, with the mean taken from all available Period 2 assessments (> Week 8 to Week 16). The primary analysis population will be the Completer Population and will include an efficacy endpoint from all patients with an assessment within ± 7 days of the planned assessment. The estimated mean change in VO_{2MAX} from Baseline to Period 2 will be presented along with a 95% confidence interval of the change and the p-value. This analysis will be repeated for the percent change from Baseline of VO_{2MAX} at the end of Period 2, including the same covariates.

Descriptive statistics of the Baseline value, VO_{2MAX} at the end of Period 2 and the change and percent change from Baseline to end of Period 2 will be presented for the Completer Population.

The primary analysis and descriptive statistics table will be repeated for the MITT, and will include any imputed change in VO_{2MAX} values for patients who did not complete the study to the end of Period 2 but provided an end of Period 2 VO_{2MAX} assessment (see section 3.1.1).

Example SAS code is shown below:

```
proc mixed data=dataP2;
  class Period;
  model CHG=BASE PEXALL Period/ solution cl;
  lsmeans Period/ cl;
run;
```

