8.4 HbA1c

HbA1c data will be listed for each subject in the Safety Population with values outside the normal reference ranges flagged as low or high.

The change from Baseline to the end of Period 2 will be analyzed using an ANCOVA with a covariate of baseline HbA1c for the Completer Population.

The difference between the change from Baseline at the end of Period 1 compared to the change from Baseline at the end of Period 2 will be analyzed using an ANCOVA with a covariate of baseline HbA1c for the Completer Population.

The change from Baseline to the end of Period 1 will be analyzed using an ANCOVA with a covariate of baseline HbA1c for the Completer Population.

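### The three 6MWT models adjust for baseline VO2MAX and omit baseline 6MWT, with no reason given; the cost is mainly precision on a secondary endpoint

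*SAP*

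**What the plan says.** The protocol (8.1.2) lists 6MWT change at the end of Period 2, and its comparison with Period 1, among the secondary endpoints. Protocol 8.4.3 leaves the secondary methods to the SAP.

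The SAP specifies three 6MWT models:

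- 7.2.3, the Period 2 model, reads: "The change from Baseline in the 6MWT at the end of Period 2 will be analyzed using an ANCOVA with covariates of baseline". The baseline it goes on to name is that of the exercise test; the covariate list in full is "ANCOVA with covariates of baseline VO₂MAX and the Period 2 mean plasma PEX level".
- 7.2.4, Period 1 against Period 2: "covariates of baseline VO₂MAX and the Period-mean plasma PEX level Completer Population and repeated for the MITT".
- 7.2.5, the Period 1 model, reads: "The change from Baseline in the 6MWT at the end of Period 1 will be analyzed using an ANCOVA with covariates of baseline". Here too the baseline named is that of the exercise test, and the Period 1 mean PEX level joins it.

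The endpoint's own baseline is available. SAP 3.1.2 says: "A 6-minute walk test (6MWT) was to be performed at the Baseline (Day 1) assessment", and the change is derived from that value.

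Elsewhere the baseline covariate matches the endpoint. SAP 7.1 analyses VO2MAX change with "covariates of baseline VO_{2MAX} and the mean plasma PEX level", and 7.2.1 and 7.2.2 do likewise. SAP 8.4 says HbA1c change "will be analyzed using an ANCOVA with a covariate of baseline HbA1c for the Completer Population".

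SAP 12, item 3, explains the move from t-test to ANCOVA: "The intention was to allow covariate adjustment for a Baseline value, to adjust for baseline severity". It does not say which baseline belongs to which endpoint.

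**The concern.** A change score usually depends on where the patient started on the same test, so the endpoint's own baseline is normally the most useful baseline covariate. The 6MWT models leave it out and use the baseline of a different test. The wording matches the VO2MAX paragraphs just before them, so carry-over is plausible, but the SAP does not settle whether the choice was deliberate.

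Three things are at stake:

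- The interval and p-value for a stated secondary endpoint.
- The point estimate of the MITT period comparison, because there the two periods can contain different patients.
- Reproducibility. The example code in 7.1 and 7.2.1 uses a generic term BASE, and no code is given for the 6MWT. A programmer who reuses that template on 6MWT records could take BASE to be baseline 6MWT, against the text.

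**Working it through.** **1. The plan's own figures.** The documents give no power, effect size, SD or correlation for the 6MWT. The VO2MAX figures in SAP 11 reproduce with a two-sided one-sample t-test (n = 30, alpha 0.05, noncentral t, 29 df): 2.0/2.5 gives 98.8% (stated as above 95%) and 1.2/2.5 gives 71.9% (stated as 72%). Everything below on the 6MWT is an illustration under stated assumptions.

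**2. Single-period means (7.2.3, 7.2.5).** With one arm, the least-squares mean at the covariate means equals the raw mean change, whichever baseline is used. A simulated data set of 30 patients confirms this: 0.4926 with either covariate. Only the standard error differs, 0.154 with VO2MAX and 0.145 with 6MWT.

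**3. Completer period contrast (7.2.4).** Each completer contributes both periods, so baseline is identical across periods. The baseline covariate can act only through the residual variance and its correlation with the PEX covariate.

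**4. Precision.** Let r be the correlation of 6MWT change with baseline 6MWT, and k the correlation of baseline VO2MAX with baseline 6MWT. Assume VO2MAX relates to 6MWT change only through baseline 6MWT. Relative to the unadjusted SD, the residual SD is sqrt(1 - r^2) with baseline 6MWT and sqrt(1 - (k r)^2) with baseline VO2MAX. Both models have the same residual degrees of freedom, so the ratio of CI widths is the ratio of these two terms:

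| r | k | own baseline | VO2MAX | ratio | CI narrower by |
|---|---|---|---|---|---|
| -0.3 | 0.2 | 0.954 | 0.998 | 0.956 | 4% |
| -0.3 | 0.9 | 0.954 | 0.963 | 0.991 | 1% |
| -0.5 | 0.2 | 0.866 | 0.995 | 0.870 | 13% |
| -0.5 | 0.9 | 0.866 | 0.893 | 0.970 | 3% |

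In terms of power, borrow a standardized effect of 0.48 (1.2/2.5, the VO2MAX Period 1 assumption), with n = 30 and 27 residual df. At r = -0.3, power is 75.7% with baseline 6MWT and 72.1% to 74.9% with VO2MAX (k from 0.3 to 0.9). At r = -0.5 it is 83.3% against 72.7% to 81.0%.

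**5. MITT period contrast (7.2.4).** Attrition is taken as planned: 33 patients, then 30. Assume no true period difference, a slope of -0.2 m of change per m of baseline, baseline SD 100 m, residual SD 45 m, no PEX covariate, and weaker walkers dropping out. These imply SD of change sqrt(45^2 + 20^2) = 49.2 m and r = -20/49.2 = -0.41, inside the range used in step 4.

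- Extreme case, the three weakest leave. The cut is at z = -1.335, the lowest 3/33. Mean baseline of those who stay rises by 0.1636/(30/33) = 0.180 SD, or 18.0 m.
- Unadjusted bias: -0.2 x 18.0 = -3.6 m.
- Adjusting for VO2MAX removes a fraction k^2, leaving -3.6 x (1 - k^2): -2.7 m at k = 0.5 and -1.8 m at k = 0.7. Over k from 0.2 to 0.9 the range is -3.5 to -0.7 m.
- A separate simulation at the same attrition, slope and SDs gave -1.0 to -1.9 m at k from 0.5 to 0.7.
- With baseline 6MWT as covariate, the bias is about 0.
- Standard error, treating records as independent: 49.2 x sqrt(1/33 + 1/30) = 12.4 m before covariate adjustment, and about 12 m after it.

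So the uncorrected part is about -1 to -3 m, or roughly 0.1 to 0.25 of a standard error.

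**The case against.** The strongest defence is that SAP 12 speaks of a baseline value to adjust for severity and does not promise each endpoint its own baseline. VO2MAX is the trial's functional measure and the entry criterion for exercise limitation (protocol 4.2.2), so it could serve as a common severity marker. Nor is own-baseline adjustment universal in the SAP: the QTcF ANCOVA in 8.6 names no covariate. This stands to the extent that SAP 12 cannot be read as requiring baseline 6MWT, and copy-over remains an inference. It does not supply a stated reason, and it does not explain why the endpoint's own baseline is left out altogether.

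A reader might also infer that omitting baseline 6MWT leaves regression to the mean in the reported 6MWT changes. It does not follow for 7.2.3 and 7.2.5: the mean at the covariate means is the same with either baseline, so the substitution removes nothing from it. Patients were in any case selected on VO2MAX and not on walking distance.

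A larger drop-out bias is also tempting to claim, but the documents plan for about 30 of 33 to complete. Withdrawing patients are asked for a 6MWT (protocol 6.11), and early assessments enter the MITT analyses (SAP 3.1.2 and 12, item 2). Both limit how far the two periods' patients differ.

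**Conclusion.** The inconsistency is real and verifiable from the text: three 6MWT models name another test's baseline, omit their own, and give no reason. High confidence attaches to that observation only. The size is modest and rests wholly on assumed correlations, slope and SDs. Low baseline correlation between VO2MAX and 6MWT makes the precision loss larger; high correlation makes it nearly vanish. The MITT effect additionally needs drop-out related to walking distance, and even then it is small beside its standard error. The documents do not support a claim that the single-period means are biased or that the completer contrast is distorted by baseline imbalance. The primary endpoint is not touched. Low-to-moderate priority.

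**What to change.** In SAP 7.2.3, 7.2.4 and 7.2.5, replace baseline VO2MAX with baseline 6MWT distance (the Day 1 value). If VO2MAX is wanted as a severity marker, add it as a further covariate and state why. Specify in the 6MWT programs that BASE means baseline 6MWT.

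The cost is one variable name in three paragraphs and the matching programs. No new data, visits or patients are needed. SAP 1 allows revision before database lock with the reason given in the study report. Made then, the change is pre-specified; made after the results are seen, it would look data-driven.
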